5. SUBJECT SELECTION

5.1. STUDY POPULATION

Up to 1,350 subjects will be enrolled in the study.

5.2. INCLUSION CRITERIA

Each subject must meet the following Inclusion Criteria:

1. Completed participation in either of the two double-blind simufilam phase 3 studies (PTI-125-06 or PTI-125-07) or Week 52 in PTI-125-10 (for subjects re-entering the study).

2. Capable of providing either written informed consent or, if incapable of written consent, permission to participate can be obtained from a Legally Authorized Representative (LAR). Verbal assent to the study procedures and schedule is required of all participants. If, in the Investigator's judgment, a subject loses capacity to consent during the duration of the study, an LAR must consent on behalf of the subject. All consent processes must be undertaken prior to any study procedures.
3. Clinical presentation continues to be consistent with Alzheimer's disease.
4. MMSE score ≥ 11 at the PTI-125-07 Week 52 or PTI-125-06 Week 76 visit (for new PTI-125-10 participants at Study Day 1).
5. Male subjects must be willing to continue use of contraception during the study. With female partners of childbearing potential, male subjects, regardless of their fertility status, must agree to either remain abstinent or use condoms in combination with one additional highly effective method of contraception (e.g., oral or implanted contraceptives, or intrauterine devices) or an effective method of contraception (e.g., diaphragms with spermicide or cervical sponges) during the study and for 14 days after study drug dosing has been completed.
6. Fluency in a language of the research site and the utilized assessment materials.
7. Continues to have adequate visual and auditory acuity (in the Investigator's judgment) that is sufficient to complete all scheduled assessments (eyeglasses and hearing aids are permitted).
8. Fully vaccinated against COVID-19.
9. Availability of a person (a study partner) who, in the Investigator's opinion, has frequent and sufficient contact with the study subject (defined as ≥ 10 hours per week), and can:
 - a. provide accurate information regarding the study subject's cognitive and functional abilities,
 - b. agree to comply with and participate at all scheduled visits and study procedures,
 - c. sign the necessary consent form,
 - d. maintain the same level of interaction with the study subject throughout the study duration.

5.3. EXCLUSION CRITERIA

Subjects meeting any of the following criteria will be excluded from the study:

1. Residence in a skilled nursing facility requiring 24-hour care (Note – subjects may reside in an assisted living facility if they do not need 24-hour care).

2. Evidence of a neurologic condition other than AD that, in the judgment of the Investigator, significantly contributes to the subject's dementia. This may include, but is not limited to, frontotemporal dementia, dementia with Lewy bodies, Parkinson's disease, corticobasal degeneration, Creutzfeldt-Jakob disease, progressive supranuclear palsy, Huntington's disease, or normal pressure hydrocephalus.
3. Subjects with any current, clinically significant psychiatric diagnosis other than AD if, in the judgment of the Investigator, the psychiatric disorder or symptom is likely to confound interpretation of drug safety or affect the subject's ability either to comply with study procedures or to complete the study.
4. New diagnosis of severe major depression even without psychotic features.
5. Significant risk for suicide. Affirms suicidal ideation in response to questions number 4 or 5 in the C-SSRS during the past 3 months (i.e., "active suicidal ideation with some intent to act, without specific plan," or "active suicidal ideation with specific plan and intent") or affirms any of the questions contained in the Suicidal Behavior section of the C-SSRS as applicable during the past 12 months.
6. Any diagnosed malignancy in the preceding phase 3 study or since previous study participation concluded in PTI-125-10, unless approved by the Medical Monitor.
7. The subject has experienced a serious adverse event during the preceding phase 3 study that presents an increased safety risk during this open-label extension study.
8. The subject has a moderate or severe ongoing adverse event from the preceding phase 3 study considered a potential safety risk in the judgment of the Investigator.
9. Clinically significant abnormality in the past 90 days on any clinical laboratory test that could impact safety in the judgment of the Investigator.
10. An unstable medical condition that is clinically significant in the judgment of the Investigator, including significant neurologic, hepatic, renal, endocrinologic, cardiovascular, gastrointestinal, pulmonary, hematologic, immunologic or metabolic disease. For participants that re-enter the study, any significant illness or hospitalization that occurred during the gap period must be discussed with the medical monitor to confirm eligibility.
11. Any other medical or neurological condition (other than Alzheimer's disease), that, in the opinion of the Investigator, might represent a contributing cause to the subject's cognitive impairment, or affect subject safety, ability to comply with study assessments, drug compliance and completion of the study.
12. Use of aducanumab, lecanemab, or any anti-amyloid monoclonal antibody.
13. Medications that in the Investigator's opinion may contribute to cognitive impairment, put the subject at higher risk for AEs, or impair the subject's ability to perform

cognitive testing or other study procedures should be discussed with the medical monitor.

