4. SUMMARY OF STUDY DESIGN

This is a multi-national, multi-center, fixed-dose, open-label extension study that will continue through FDA approval of simufilam or program termination ([Appendix A](#)). After completing participation in either PTI-125-06 or PTI-125-07, subjects will have the option to participate in this study. After the subject provides consent and the Investigator confirms the subject satisfies both inclusion and exclusion (I/E) criteria, the study drug will be administered at the research site on Study Day 1 and subsequent visits will be scheduled.

Subjects who already completed participation through Week 52 in PTI-125-10 will have the option to return to the study and continue participation. After the subject provides consent, the Investigator will confirm that the subject continues to satisfy both the I/E

criteria. The study drug will be administered at the research site on Re-entry Day 1 and subsequent visits will be scheduled. The length of their participation gap will dictate which visits apply to them.

We anticipate up to 1,350 subjects may enroll in this study. Approximately 170 clinical sites in the USA, Canada, the Republic of Korea, and Australia will have the option to participate in this collaborative research effort.

For subjects electing to participate, the clinical and laboratory assessments from the Week 76 (PTI-125-06) or Week 52 (PTI-125-07) End-of-Treatment visit will serve as Baseline Visit assessments for the open-label study on Study Day 1. Additional blood samples will be taken on Study Day 1 to assess Hemoglobin A1c (HbA1c) and plasma biomarkers upon receipt of required supplies. All subjects will return in 4 weeks and then every 12 weeks thereafter for safety assessments.

For subjects re-entering the study, the length of their participation gap will determine their need for clinical and laboratory assessments. A blood sample will be taken to assess HbA1c and plasma biomarkers upon receipt of required supplies.

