Information and instruction for the computer-based study management system will be covered during site training, and written reference information will be included in the pharmacy manual.

For all follow-up visits, subjects will be instructed to bring their study drug bottle to the clinic. Research staff will conduct and log the pill count, and a new bottle of study drug will be dispensed.

7.1.2. *Re-entry Day 1 (Dosing Re-initiation)*

This visit applies to all subjects who completed their original participation in the PTI-125-10 study and want to resume study participation. Subjects will come to the clinic in the morning whenever possible. Prior to dosing, the following will be completed:

- Informed Consent
- Medical History- focused on any new conditions that occurred during the gap period between study completion and study re-entry
- Adverse event monitoring
- Use of concomitant medications
- Vital signs (blood pressure [supine], temperature and pulse)
- Brief physical and neurologic examination
- Height

- Weight
- 12-lead resting ECG (5-min supine) - only for subjects who completed their PTI-125-10 Week 52 visit >60 days prior to re-entry
- Clinical laboratory tests (biochemistry, hematology, and urinalysis) - only for subjects who completed their PTI-125-10 Week 52 visit >60 days prior to re-entry
- Collect samples for HbA1c and plasma biomarkers
- CDR - only for subjects who completed their PTI-125-10 Week 52 visit >60 days prior to re-entry
- C-SSRS – Since Last Visit version
- Review of I/E criteria following all Re-entry Day 1 assessments and prior to dosing.

Once all Re-entry Day 1 procedures are completed, a 188-count bottle of study drug to be dispensed is assigned by the computer-based study management system.

Subjects will be administered one (1) tablet of study drug at the clinic at least 1 hour before departure. The subject will be discharged with their supply of study drug. The study partner will be instructed to administer study drug twice daily with or without food. The study partner should be advised that a dose can be up to 4 hours late, but, if a dose is missed, the next dose should NOT be doubled.

For all follow-up visits, subjects will be instructed to bring their study drug bottle to the clinic. Research staff will conduct and log the pill count, and a new bottle of study drug will be dispensed when required.

7.1.3. Week 4 and Re-entry Week 4

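### At re-entry, exclusion 6 requires Medical Monitor approval for a malignancy from phase 3 or from the gap, but not for one diagnosed on simufilam during the first PTI-125-10 period

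*Protocol*

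**What the plan says.** Protocol Section 5.2, inclusion 1, opens two routes into the study: completion of one of the phase 3 trials (PTI-125-06 or PTI-125-07), or, for returning subjects, completion of Week 52 in PTI-125-10 itself. Of returning subjects, Section 4 says: "After the subject provides consent, the Investigator will confirm that the subject continues to satisfy both the I/E" criteria. Section 7.1.2 places this check just before the first new dose: "Review of I/E criteria following all Re-entry Day 1 assessments and prior to dosing".

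Four exclusions in Section 5.3 matter here.

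- Exclusion 6: "Any diagnosed malignancy in the preceding phase 3 study or since previous study participation concluded in PTI-125-10, unless approved by the Medical Monitor".
- Exclusion 7: "The subject has experienced a serious adverse event during the preceding phase 3 study that presents an increased safety risk" in the extension.
- Exclusion 8: "The subject has a moderate or severe ongoing adverse event from the preceding phase 3 study" that the Investigator considers a potential safety risk.
- Exclusion 10 has two parts. The first sentence excludes unstable, clinically significant conditions in the Investigator's judgment. The second applies to re-entrants only: "any significant illness or hospitalization that occurred during the gap period must be discussed with the medical monitor to confirm eligibility".

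Exclusion 11 is a catch-all. It covers any other condition that, in the Investigator's opinion, might contribute to the cognitive impairment or "affect subject safety, ability to comply with study assessments, drug compliance and completion of the study".

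**The concern.** A re-entrant passes through three periods before Re-entry Day 1: the phase 3 study, the first PTI-125-10 period on open-label simufilam, and the gap. Exclusion 6 names the first and the third. Read literally, it asks for Medical Monitor approval of a malignancy found while the subject was off drug in the gap, and not of one found while the subject was on drug just before it.

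What is at stake is a safety sign-off on restarting an investigational drug. Section 2.2 describes the carcinogenicity programme as unfinished, with the mouse study still dosing and the rat study being reported. In that setting an on-drug malignancy deserves at least the review given to an off-drug one.

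**Working it through.** No arithmetic applies. The check sets each look-back window against the re-entrant's timeline.

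| Period before re-entry | Study drug | Exclusion 6 (malignancy) | Exclusion 7 (risk-raising SAE) | Exclusion 10, second sentence |
|---|---|---|---|---|
| Phase 3 study | Simufilam or placebo | Covered; approval needed | Covered | Not covered |
| First PTI-125-10 period, Study Day 1 to Week 52 | Simufilam 100 mg b.i.d. (Section 6.2) | Not covered | Not covered | Not covered |
| Gap | Off drug (Section 7.1.2 is a dosing re-initiation visit) | Covered; approval needed | Not covered | Covered; discussion needed |

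The first PTI-125-10 period is the only row that none of the three rules reaches.

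**Could the phase 3 wording include PTI-125-10?** No. Inclusion 1 identifies the phase 3 studies as PTI-125-06 and PTI-125-07 and lists PTI-125-10 separately. Exclusion 7 itself contrasts the phase 3 study with the present extension.

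**Can such a subject reach re-entry?** Yes. Re-entry requires completing Week 52, so anyone who left early because of a malignancy is out. But malignancy is not among the stopping criteria in Section 7.1.9 (liver tests, C-SSRS findings, weight loss with low BMI), and withdrawal under Section 10 is discretionary. A subject whose malignancy was treated could complete Week 52 and qualify.

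**What else would catch a malignancy?** Mainly exclusion 10, first sentence, if the condition is unstable, and exclusion 11, if the Investigator thinks it might affect safety. Neither requires the Medical Monitor. If the malignancy led to significant illness or hospitalization in the gap, the second sentence of exclusion 10 would bring the medical monitor in. The Re-entry Day 1 history is focused on the gap but not confined to it, so an earlier diagnosis may also surface there.

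**What else would catch a first-period SAE?** More than for malignancy. Exclusions 2 to 5 cover certain neurological, psychiatric and suicidality findings. Exclusion 9 covers clinically significant laboratory abnormalities in the past 90 days. Exclusions 10 and 11 cover current conditions, and Section 7.1.9 deals with some liver and suicidality events when they occur. What may slip through is a resolved SAE that still raises the risk of further dosing.

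**Ongoing adverse events (exclusion 8).** Exclusions 10 and 11 largely cover these already, so changing exclusion 8 would be for consistency only.

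**The case against.** The strongest defence is that the sponsor already knew about first-period events. Adverse events were recorded (Section 11.1), SAEs went to pharmacovigilance within 24 hours (Section 11.5), the Sponsor was told at once of any decision to stop drug because of an event (Section 7.1.8), and a DSMB followed safety (Section 4). The gap is the interval without study visits, so asking the Medical Monitor about that interval has some logic. This shows that the events are not hidden, but it does not explain the pattern. Phase 3 events also arose in the sponsor's own trials, and exclusion 6 still demands approval for them.

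A second defence is parity. A continuing participant with the same malignancy passes Week 52 with no eligibility review, because Appendix B schedules that review only on Study Day 1. This stands as a cost of the fix. It does not justify the present rule, because re-entry is a new consent and a new decision to dose, at which the protocol chose to apply the criteria again.

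A third is that exclusion 7 is a weaker case. That is right. It has no Medical Monitor step and omits the gap as well, so the contrast between on-drug and off-drug time belongs to exclusion 6 alone.

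A reader might infer three stronger things. One is that first-period malignancies go unscreened at re-entry; exclusions 10 and 11 show otherwise. Another is that the drug carries a cancer signal; Section 2.2 reports none, and the genotoxicity battery was negative. The third is that the omission was deliberate, or that it was careless; the documents do not give the reason.

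**Conclusion.** The point holds for exclusion 6 as worded: at re-entry, a malignancy diagnosed during the first PTI-125-10 period needs no Medical Monitor approval, while one from phase 3 or from the gap does. Exclusion 7 has a related but secondary shortfall, limited mainly to resolved SAEs that still raise risk.

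Severity is minor. No analysis set, endpoint or analysis is affected. The number of subjects concerned cannot be derived: the protocol's ceiling of 1,350 and the SAP's 1081 participants are totals, and neither document counts re-entrants or their malignancies. One could express the uncovered period as a share of time on drug, but that would only restate nominal study lengths and would say nothing about risk.

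The conclusion assumes that the subject was dosed in the first period and off drug in the gap, and that participation concluded at about Week 52. If it is taken to conclude at the follow-up call, 7 to 14 days after the last dose, the uncovered window runs slightly longer.

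**What to change.** Reword the look-back in exclusion 6 to: *in the preceding phase 3 study, or during or since previous participation in PTI-125-10, unless approved by the Medical Monitor*. In exclusion 7, and in exclusion 8 for consistency, extend the look-back to: *the preceding phase 3 study or, for re-entering subjects, during or since previous participation in PTI-125-10*. The words *or since* are needed in exclusion 7 because it currently omits the gap too.

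The change adds no procedure for first-period events, which are already in the study's adverse event records. A few re-entrants would need extra review, and re-entrants would be screened more strictly than continuing participants with the same history. Any amendment needs IRB approval before use (Section 14.5.1), and Section 4 foresees approximately 170 sites in four countries, so the edit is best carried with other changes and not issued alone. SAP Section 10 records early termination by the sponsor, so its practical place is a further amendment, if there is one, or a successor extension protocol.

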6. STUDY DRUG

6.1. SIMUFILAM PHYSICAL DESCRIPTION AND PREPARATION

Investigational simufilam (100 mg active strength) will be supplied by Cassava as coated oral tablets.

6.1.1. Packaging and Labelling

Simufilam tablets in plastic bottles will be supplied in 70-count bottles for a 4-week supply or 188-count bottles for a 12-week supply. Bottles include a desiccant canister and are closed with a foil seal and child-resistant (CR) cap. Each bottle contains 7 or 10 days of extra medication to accommodate scheduling flexibility with clinic visits.

Each bottle is open-labeled and includes a unique Medication ID number that is referenced for dispensing investigational drug. A computer-based clinical study management system will specify the Medication ID number to be dispensed to the subject at clinical visits.

6.1.2. Storage

The investigational drug supplies must be stored in a locked cabinet or room with limited access at controlled room temperature, 20-25° C (68-77° F) and protected from moisture.

6.1.3. Drug Accountability

The Investigator will be responsible for monitoring the receipt, storage, dispensing and accounting of all study drug according to the site's standard operating procedures (SOPs). All records documenting the chain of custody for the study drug must be retained in the site study file. Accurate, original site records must be maintained for study drug inventory and dispensing. All records must be made available to the Sponsor (or designee) and appropriate regulatory agencies upon request.

All remaining unused simufilam study drug will be returned to the Sponsor or designee.

6.2. ADMINISTRATION AND DOSING REGIMEN

Subjects will receive 100 mg simufilam tablets for twice daily (b.i.d.) oral administration. Study drug can be taken with or without food.

6.3. CONCOMITANT MEDICATIONS

Use of prescription or non-prescription medications will be recorded during the study.

7. STUDY PROCEDURES

Appendix B presents the Schedule of Activities for New/Active Participants. Appendix C presents the Schedule of Activities for Re-Entry Participants.

Prior to any study-related activity, the Informed Consent Form (ICF) must be signed and dated by the subject (or a LAR) and the study partner. The format and content of the ICF must be agreed upon by the Principal Investigator(s), the appropriate IRB and the Sponsor. The signed and dated ICF must be retained by the Investigator in the subject's file.

7.1. EVALUATIONS BY VISIT

Follow-up visits can be scheduled +/- five (5) days from the targeted Study Visit date.

7.1.1. *Study Day 1 (Dosing Initiation)*

The clinical and laboratory assessments performed at the Week 76 (PTI-125-06) or Week 52 (PTI-125-07) End-of-Treatment visit will serve as the baseline (Study Day 1) for this open-label extension study. Subjects will come to the clinic in the morning whenever possible. Prior to dosing, the following will be completed:

- Informed Consent
- Height (to facilitate BMI calculation)
- Collect samples for HbA1c and plasma biomarkers
- Review of I/E criteria following all Study Day 1 assessments and prior to dosing.

From the Week 76 or Week 52 End-of-Treatment visit (PTI-125-06 or PTI-125-07, respectively) in the phase 3 study in which the subject participated:

- Review of concomitant medications
- Adverse Event Monitoring
- C-SSRS – Since Last Visit version
- Vital signs (blood pressure [supine], temperature, pulse)
- Weight
- Brief physical and neurologic examination (Note: the brief physical and neurologic examination performed on Study Day 1 and at all subsequent visits will include an assessment of the following: general appearance; cardiovascular, pulmonary, and abdominal examination, as well as an examination of any other system in response to subject-reported symptoms; cranial nerves [II-XII], tone, power, deep tendon reflexes, coordination and gait)

- Clinical laboratory tests (biochemistry, hematology, and urinalysis)
- 12-lead resting ECG (5-min supine)
- CDR

If the Study Day 1 (baseline) visit does not coincide with the Week 76 or Week 52 End-of-Treatment visit for the double-blind study (PTI-125-06 or PTI-125-07, respectively), the Investigator should confer with the Medical Monitor to determine whether selected assessments may need to be repeated.

Once all Study Day 1 procedures and assessments have been completed, the 70-count bottle of study drug to be dispensed is assigned by the computer-based study management system.

Subjects will be administered one (1) tablet of study drug at the clinic at least 4 hours after any prior dose and at least 1 hour before departure. The subject will be discharged with their supply of study drug. The study partner will be instructed to administer study drug twice daily with or without food. The study partner should be advised that a dose can be up to 4 hours late, but, if a dose is missed, the next dose should NOT be doubled.

Information and instruction for the computer-based study management system will be covered during site training, and written reference information will be included in the pharmacy manual.

For all follow-up visits, subjects will be instructed to bring their study drug bottle to the clinic. Research staff will conduct and log the pill count, and a new bottle of study drug will be dispensed.

7.1.2. *Re-entry Day 1 (Dosing Re-initiation)*

This visit applies to all subjects who completed their original participation in the PTI-125-10 study and want to resume study participation. Subjects will come to the clinic in the morning whenever possible. Prior to dosing, the following will be completed:

- Informed Consent
- Medical History- focused on any new conditions that occurred during the gap period between study completion and study re-entry
- Adverse event monitoring
- Use of concomitant medications
- Vital signs (blood pressure [supine], temperature and pulse)
- Brief physical and neurologic examination
- Height

- Weight
- 12-lead resting ECG (5-min supine) - only for subjects who completed their PTI-125-10 Week 52 visit >60 days prior to re-entry
- Clinical laboratory tests (biochemistry, hematology, and urinalysis) - only for subjects who completed their PTI-125-10 Week 52 visit >60 days prior to re-entry
- Collect samples for HbA1c and plasma biomarkers
- CDR - only for subjects who completed their PTI-125-10 Week 52 visit >60 days prior to re-entry
- C-SSRS – Since Last Visit version
- Review of I/E criteria following all Re-entry Day 1 assessments and prior to dosing.

Once all Re-entry Day 1 procedures are completed, a 188-count bottle of study drug to be dispensed is assigned by the computer-based study management system.

Subjects will be administered one (1) tablet of study drug at the clinic at least 1 hour before departure. The subject will be discharged with their supply of study drug. The study partner will be instructed to administer study drug twice daily with or without food. The study partner should be advised that a dose can be up to 4 hours late, but, if a dose is missed, the next dose should NOT be doubled.

For all follow-up visits, subjects will be instructed to bring their study drug bottle to the clinic. Research staff will conduct and log the pill count, and a new bottle of study drug will be dispensed when required.

7.1.3. Week 4 and Re-entry Week 4

While the Week 4 visit is required for all newly enrolled participants, the Re-entry Week 4 visit applies only to re-entry subjects whose gap period between previous and current participation is >60 days. Subjects will return to clinic for these scheduled visits within a \pm 5-day “window.” The following will be completed:

- Adverse event monitoring
- Use of concomitant medications
- Vital signs (blood pressure [supine], temperature and pulse)
- Brief physical and neurologic examination
- Height
- Weight
- 12-lead resting ECG (5-min supine)

- Clinical laboratory tests (biochemistry, hematology, and urinalysis)
- C-SSRS – Since Last Visit version
- Receive and count remaining tablets in each bottle of investigational product to assess adherence to BID dosing.

For Week 4 visits only, a 188-count bottle of study drug to be dispensed is assigned by the computer-based study management system. For Re-entry Week 4, the bottle that was previously dispensed at Re-entry Day 1, will be returned to the subject following study drug accountability.

